1. PROTOCOL SYNOPSIS

NAME OF PRINCIPAL INVESTIGATOR: [name], MPH	PROTOCOL NUMBER: JKB121-001 (Version 4.0)
NAME OF SPONSOR TaiwanJ Pharmaceuticals Co., Ltd	
NAME OF FINISHED PRODUCT: JKB-121	IND 124,082
NAME OF ACTIVE INGREDIENT: Nalmefene hydrochloride	
Study Title	A Randomized, Double-Blind, Placebo Controlled, Parallel-Group, Phase II Trial of JKB-121 for the Treatment of Nonalcoholic Steatohepatitis (NASH).
Lead Investigator:	[name], MPH Duke University
Number of Centers:	Approximately 12 sites—United States only
Study Phase	II
Study Objectives:	
Primary Objectives:	To evaluate the safety and potential efficacy of two dose levels of JKB-121 (5 mg twice daily and 10 mg twice daily) in reducing liver fat compared to placebo.
Secondary Objective:	The secondary objectives are 
Determine the pharmacokinetic profile of JKB-121 in NASHAssess the impact of treatment with JKB-121 on metabolic markersAssess the impact of treatment on liver enzymes (serum ALT) over 24 weeks.Establish the recommended dose for future NASH treatment studies.To evaluate changes of NASH related biomarkers such as adiponectin, leptin, ghrelin, TNF-alpha, TGF-beta, hyaluronic acid and MMP-2.
Exploratory Objective	Investigate the impact of treatment of potentially relevant inflammatory and metabolic biomarkers associated with NASH
Study Endpoints:	
Primary Endpoints:	Safety: Incidence and severity of adverse events and changes in vital signs and clinical laboratory tests Efficacy: Comparative changes in 
Mean changes from baseline in the percentage fat content of the liver measured by magnetic resonance imaging (MRI) at week 24.
Secondary Endpoints:	Pharmacokinetics: 
Serum concentration of JKB-121 over time including but not limited to maximum observed concentrations (Cmax), minimum observed concentration (Cmin) and area under the concentration time curve (AUC) and if feasible half-life (t½) Metabolic markers: 
Body mass index (BMI)

	
• HbA1c and the homeostatic model assessment of insulin resistance (HOMA-IR)• Serum lipid profile: total cholesterol, triglycerides, low density lipoprotein (LDL) and high density lipoprotein (HDL) fractions. 
Liver Function:
 
• Mean change from baseline in serum ALT at week 24.• Mean serum aspartate aminotransferase (AST), alanine aminotransferase (ALT), and gamma-glutamyl transpeptidase (GGT) at weeks 4, 8, 12, 16, 20, and 24.• Proportion of subjects whose ALT level at week 24 is within normal range defined as < 20 U/L for women and < 30 U/L for men.
Exploratory Outcome Measures:	
• Mean serum concentrations of lipopolysaccharide (LPS), c-reactive protein (CRP), cytokeratin (CK)-18 fragments, proinsulin c-peptide, glucagon-like polypeptide (GLP-1) and adiponectin.• Relative levels of inflammatory cytokines, interferon gamma (IFN-γ), and tumor necrosis factor alpha (TNF-α)• Relative levels of regulatory T cells in the peripheral blood mononuclear cells (PBMC) samples including CD4, CD8, CD 25, Fox P3, NKT, and CD62 T cells.
Methodology:	
Study design	Randomized double blind, placebo control 3-arm parallel group, multi-dose single center study
Study duration	Up to 28 days for screening, 24 weeks of treatment and 28 days of follow-up. Subjects terminating study drug will be followed-up post-treatment for 28 days.
Number of Subjects:	The study will aim to recruit 60 subjects, randomized 1:1:1
Stratification:	Treatment allocation will be stratified by known diagnosis of diabetes status. Nondiabetic status will be defined as HbA1c \leq 6.0 and absence of any medications to treat diabetes. Diabetic status will be defined as HbA1c $>$ 6.0 and/or requiring medication for treatment of diabetes mellitus.
Study Drug:	JKB-121 oral tablet
Control Group	Placebo to match
Dose Regimens	Arm A: 5 mg JKB-121 twice daily. Arm B: 10 mg JKB-121 twice daily Arm C: Matching placebo twice daily All treatment dose regimens are administered per orally
Administration: Schedule:	Twice daily for 24 weeks

Study Population:	Adults with biopsy-proven nonalcoholic steatohepatitis (NASH)
Inclusion Criteria:	
 1. Age \geq 18 years 2. Provision of written informed consent 3. Biopsy-proven NASH within 12 months prior to randomization verified by central pathology reading with: 
 • NASH activity score (NAS) of 4 or more • 10% or more macrovesicular steatosis • cytologic ballooning score of at least 1 point • hepatic fibrosis of at least 1 point • hematoxylin and eosin (H&E) stained slides and/or paraffin block available for independent assessment 4. ALT $>$ 40 U/L for women and $>$ 60 U/L for men at screening and at least once in the previous 12 months. 5. MRI with $>$ 6% hepatic steatosis 6. HbA1c of \leq 9.0 7. Lipid lowering agents (i.e. statins) and allowable antidiabetic treatment (i.e. metformin or sulfonylurea) must be stable at screening and during the study. 8. Agree to use of effective contraceptive measures if female of child bearing potential.
Exclusion Criteria:	
 1. Any chronic liver disease other than NASH (i.e., drug-induced, viral hepatitis, autoimmune hepatitis, primary biliary cirrhosis, primary sclerosing cholangitis, hemochromatosis, A1AT deficiency, Wilsons disease) 2. Cirrhosis, as assessed clinically or histologically (fibrosis stage 4) 3. Presence of vascular liver disease 4. BMI \leq 25 kg/m² 5. Excessive alcohol use ($>$ 20 g/day) within the past 2 years 6. AST or ALT $>$ 250 U/L 7. Type 1 diabetes mellitus 8. Bariatric surgery in the past 5 years. 9. Weight gain or weight loss of $>$ 5% in past 6 months or $>$ 10% change in past 12 months. 10. Contraindication to MRI 11. Inadequate venous access 12. HIV antibody positive, hepatitis B surface antigen positive (HBsAg), or HCV RNA positive. 13. Receiving an elemental diet or parenteral nutrition 14. Chronic pancreatitis or pancreatic insufficiency 15. Any history of complications of cirrhosis (i.e. ascites, hepatic encephalopathy, or portal hypertensive bleeding), even if absent or optimized with medical management at time of screening 16. Concurrent conditions: 
 a) Inflammatory bowel disease b) Unstable angina, myocardial infarction, transient ischemic events, or stroke within 24 weeks of screening c) Ongoing infectious, immune mediated disease within previously 1 years d) Any malignant disease (other than basal cell carcinoma of the skin) within previous 2 years e) Prior solid organ transplant

	
f) Any other concurrent condition which, in the opinion of the investigator, could impact adversely on the subject participation or the interpretation of the study data.
 
17. Concurrent medications including:
 
a) Anti-NASH therapy(s) initiated after the liver biopsy diagnosing NASH. Anti-NASH therapies include S-adenosyl methionine (SAMe), milk thistle, and vitamin E.b) Antidiabetic medication which may impact NASH histology initiated after the liver biopsy diagnosing NASH including thiazolidinediones (glitazones), dipeptidyl peptidase 4 inhibitors (gliptins) or glucagon-like peptide 1 analogs.c) Immune modulatory agents including systemic steroids, methotrexate, anti-TNF-α therapies (infliximab, adalimumab, etanercept) or anti-integrin therapy (namixilab).d) UGT2B7 enzyme inhibitors (e.g., diclofenac, fluconazole, medroxyprogesterone acetate, meclofenamic acid)e) UGT2B7 inducers (e.g., dexamethasone, phenobarbital, rifampicin, omeprazole)f) Chronic opioid use within 28 days prior to screening (Day -28) 
18. Self-reported or known marijuana or illicit drug use within 28 days before the screening
 
19. The following laboratory abnormalities:
 
a) HbA1c > 9.0%b) Neutrophil count < 1.0×10^9 / Lc) Platelets < 100×10^9 / Ld) Hemoglobin < 10 g/dle) Albumin < 3.5 gf) International normalized ratio (INR) > 1.3g) Any elevation of total bilirubin above normal (unless Gilbert's syndrome or extrahepatic source as denoted by increased indirect bilirubin fraction).h) Serum creatinine > 1.5 mg/dli) Creatinine clearance \leq 50 ml/minute calculated by Crockroft-Gault. 
20. Pregnancy or breastfeeding.
 
21. Women, of childbearing age, who are not willing to practice effective contraception (i.e., barrier, oral contraceptives, or past medical history of hysterectomy) for the 48-week duration of the trial and for 1 month after the last administration of the drug. Women with documented (not reported) oophorectomy or hysterectomy are considered sterile. Women with tubal ligation are at small risk and should have pregnancy test at screening.
 
22. Participation in an investigational drug study within past 30 days.

--	---

Study Procedures and Visit Schedule:	
Refer to Table 1 for the schedule of study procedures.
 
Subjects who provide voluntary written informed consent will be screened for eligibility. Subjects meeting all the inclusion and none of the exclusion criteria will be eligible to participate.
 
The maximum time on study drug for each subject is 24 weeks with an additional 4 weeks of follow-up.
 
Eligible subjects will be randomized at the baseline visit to receive one of three study treatments twice daily for a period of 24 weeks. Each subject will return for assessment and required study procedures on days 14, 28 and every 4 weeks thereafter until week 24. A final follow-up visit will be conducted at week 28 if the subject ceases treatment at week 24.
 
Investigational product dispensing and accounting will be conducted on a 4 week basis.
 
The actual visit schedule will be as follows:
 
• Screening period, culminating in randomization (screening assessments must be completed no more than 4 weeks prior to enrollment).• Baseline visit and every 4 weeks afterward for total of 24 weeks• Week 8, 16 and 24 (\pm 4 days) visits will include measure of metabolic (glucose, lipids, glycosylated hemoglobin, HOMA-IR, C-reactive protein etc.)• Week 12 and 24 (\pm 4 days) will include measures of hepatic steatosis and exploratory measures (i.e. CK-18, adiponectin, leptin, ghrelin, TNF-α, TGF-β, hyaluronic acid, cytokines, and MMP-2 etc)• Follow-up visit at week 28 (\pm 4 days).• Unscheduled or early withdrawal visits may be necessary.
Safety Assessment	
Safety Parameters:	
The following measures of safety and tolerability will be conducted at screening, baseline and every 4 weeks during the study:
 
• Adverse event monitoring• Physical examination including vital signs• Safety laboratory assessments• Treatment compliance• Urine pregnancy test (women only) 
The following measures of safety and tolerability will be conducted at screening, baseline and every 12 weeks during the study:
 
• Electrocardiogram (EKG)• Urinalysis
Other Parameters:	
The following measures of immunological profile will be explored in this study:
 
• Insulin resistance (HOMA-IR, insulin and glucose levels, HbA1c)• Lipid levels• Special laboratory functions panel include CK-18, adiponectin, leptin, ghrelin, TNF-α, TGF-β, hyaluronic acid, and MMP-2.

Statistical Considerations:

Sample Size Determination:

An approximate total of 60 subjects will be enrolled. Subjects will be randomized into three treatment groups in a ratio of Group 1 (5 mg twice daily): Group 2 (10 mg twice daily): Group 3 (placebo twice daily) = 1:1:1. No empirical power calculation is performed. The sample size is based on the best medical judgment.

The power to detect a difference between placebo and active treatment with respect to change from baseline in liver fat content and serum ALT has been determined for a sample size of 20 patients per arm to assess safety and potential efficacy. Fat quantification by MRI is very sensitive with as small as a 5% detectable change in fat quantification.

Further, since the endpoint is the change from baseline, plausible estimates of the degree of correlation between pre-and post-baseline measurements will be incorporated into the variance estimates. Given the wide range of results observed in the literature, several “what-if” scenarios were examined. As such, the current sample size was considered sufficient for the exploratory objectives of the study for the given range of plausible treatment effects and variance estimates. Due to the exploratory objects of the protocol, no adjustment for the two co-primary endpoints was made. Additionally, there will be no adjustments for multiple comparisons between the 3 treatment groups.

Assuming the observed difference between two treatment groups is 20%, then the 95% confidence interval for the true mean is given by (2.5%, 37.5%) with 20 subjects in each group.

Fat Liver Content Change from Baseline:

The current sample size of 20 subjects per group should yield approximately 85% power to detect a treatment effect of at least ~ 5% with respect to the difference in the mean change from baseline between one of the JKB-121 treatment groups and placebo

ALT change from Baseline:

Patients will be stratified into treatment arms based on threshold of baseline elevation of ALT (i.e. ALT < 2x ULN and ALT \geq 2 x ULN, but < 5 x ULN). The current sample size of 20 subjects per group should yield approximately 73% power to detect a treatment effect of at least 30 U/L assuming a SE of 50 U/L ($\alpha = 0.05$; two tailed; unpaired t-test). The SD of 50 U/L for the change from baseline endpoint was derived assuming SDs of 40 for the pre-and post-baseline measurements with a correlation of 0.25.

Sample size and power estimates have not been adjusted for multiple comparisons or multiple endpoints, dropouts or stratifications.

The analysis of each primary endpoint will be based on a linear model that incorporates the baseline measures as a covariate, the stratification factor and randomization treatment group. Pairwise comparisons of each active treatment group to control will be conducted via linear contrasts.

Statistical Analysis	
The populations for analysis will be as follows:
 
Full Analysis Set (FAS) for Efficacy: includes all subjects who received at least one dose of study medication. Only subjects with clear documentation that no study medication was received may be excluded. In the event of allocation errors, subjects will be analyzed for efficacy according to the treatment to which they were randomized.
 
Safety Analysis Set: includes all subjects who received at least one dose of study medication. Only subjects with clear documentation that no study medication was received may be excluded. In the event of treatment allocation errors, subjects will be analyzed for efficacy according to the treatment in which they were randomized.
 
Per Protocol Analysis Set includes all subjects who complete 24 weeks of study treatment and have MRI and ALT measured at baseline and at week 24 and no major protocol violations, determined prior to break of the treatment blind.
 
All hypotheses will be tested for statistical significance with two-tailed p-values. Results of all tests will be considered statistically significant if their p-value is less than or equal to 0.05, except results of the tests for interaction will be considered statistically significant if the p-value is less than or equal to 0.10

Efficacy:	
The primary endpoint of this study is the safety and potential efficacy of two dose levels of JKB-121 (5 mg twice daily and 10 mg twice daily) in reducing liver fat compared to placebo.
 
The secondary endpoint of the study is the time to remission (TTR) is defined as time in weeks from randomization to liver aminotransferase remission as defined as two consecutive ALT values within normal range (< 20 U/L for women and < 30 U/L for men) or a 20% reduction from the baseline during study period. A Cox proportional hazard model will be used to compare the TTR duration between treatment arms.
 
Median duration of TTR and the hazard ratio with 95% confidence limits will be estimated using Kaplan-Meier survival methodology. TTR from randomization will be compared using estimates from the Kaplan-Meier survival curves. A detailed comparison of the treatment effects will be analyzed by fitting a Cox proportional hazard model with baseline variables as covariates to assess the benefit-risk ratio.

Safety:	
The primary safety endpoints will be the rates of patients who experience (1) one or more AEs; (2) SAEs; and (3) AEs leading to discontinuation of study medication. Treatment effect will be explored by inspection of observed means or rates for the dose groups within each treatment regimen. Other safety parameters such as laboratory test, vital signs, and other safety related variables will be summarized regarding each scheduled visit. Shift tables will be presented for laboratory values based on the reference laboratory normal ranges.

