10.3.1 Subject Enrollment and Treatment Assignment

After written informed consent has been obtained and eligibility to participate established, investigative site personnel will obtain the subject's identification number and study drug kit assignment from investigational drug pharmacy or IVRS/IWRS system. Patients will be stratified into treatment arms based diabetes status.

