### 4.2 Randomization and Treatments

Patients will be randomized in the order in which they are enrolled into this double-blind study by using a computer-generated randomization schedule. TaiwanJ Pharmaceuticals prepared the schedule prior to the start of the study. This number will designate which allocated treatment a patient will receive. The randomization schedule will be a ratio of 1:1:1 to one of the following three treatment groups:

- JKB-121 5 mg tablet twice daily orally
- JKB-121 10 mg tablet twice daily orally
- Placebo as tablet twice daily orally

Treatment allocation will be stratified by known diagnosis of diabetes status. Nondiabetic status will be defined as  $HbA1c \leq 6.0$  and absence of any medications to treatment diabetes. Diabetic status will be defined as  $HbA1c > 6.0$  and/or requiring medication for treatment of diabetes mellitus.

Subjects who are withdrawn from the study will not be replaced.

Until formal conclusion of the study, subjects, investigators and all site study personnel will be remain blinded as to treatment allocation, except in the event of a medical emergency which necessitates unblinding.

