### **6.5 Demographic and Baseline Characteristics**

Demographics and baseline characteristics will be summarized descriptively by treatment group and total for the Safety Population and mITT Population.

Demographic and baseline characteristics include, but are not limited to, age at informed consent, gender, race, ethnicity, body weight, body mass index (BMI), and baseline efficacy measures (percentage fat content of the liver measured by MRI, ALT, AST, GGT).

Randomization stratum (diabetic status) will also be summarized. Continuous variables will be summarized by descriptive statistics. Categorical variables will be summarized by the number and percentage of patients in corresponding categories. The baseline is defined in Section 6.2, Baseline, Endpoint, and Other Statistical Considerations.

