## 6.9 Efficacy Analysis

### 6.9.1 Primary Efficacy Endpoint

The change from baseline at Week 24 of the percentage fat content of the liver measured by MRI will be analyzed by analysis of covariance (ANCOVA) in the Full Analysis Set Population with treatment group and diabetes stratum as factors and baseline MRI value as a covariate. The comparisons will be (1) between the response of the JKB-121 5 mg group and the response of the Placebo group and (2) between the response of the JKB-121 10 mg group and the response of the Placebo group. The least-squares means, standard errors, and 95% confidence intervals for each treatment group and for each comparison will be provided. The two-sided p-values testing for significance within treatment group change from baseline and comparisons between treatment groups will be presented. No multiple comparisons techniques will be applied. The sample SAS code can be found below:

```
*****
Note:
  TREATMENT = 0, (placebo), 1 (JKB-121 5 mg), 2 (JKB-121 10 mg)
  DIABSTAT = nondiabetic, diabetic
  BASE: baseline percentage fat content of the liver measured by MRI
  CHG: change from baseline to Week 24 in the percentage fat content of
       the liver measured by MRI
*****;
proc glm data=MRI;
  class TREATMENT DIABSTAT;
  model CHG = TREATMENT DIABSTAT BASE / ss1 ss3;
  means TREATMENT;
  lsmeans TREATMENT / cov stderr pdiff cl;
  estimate "JKB-121 5 mg : Placebo" TREATMENT -1 1 0;
  estimate "JKB-121 10 mg : Placebo" TREATMENT -1 0 1;
run;
```

The data and model residuals will be inspected for normality and homogeneity of variance, and a logarithmic transformation will be applied if necessary.

To handle missing results such as due to early termination, multiple imputation will be performed. The detailed steps are specified below.

Step 1: Prepare the data for multiple imputation. Since there is only one intermediate visit (Week 12) for MRI collection, the missing pattern would be monotone if endpoint values are not available.

Step 2: PROC MI would be used to impute the missing MRI values. The treatment, diabetes stratum, and MRI values at baseline and all available post-baseline visits would be included. The SAS code can be found as below:

```
PROC MI data=MRI out=MI_OUT nimpute=1000 seed=12345 minimum=0;  
  var TREATMENT DIABSTAT BASE WEEK12 WEEK24;  
  mcmc initial=em prior=jeffreys nbiter=200 niter=500 chain=single;  
run;
```

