#### **Time to Remission**

TTR defined as the time in weeks from randomization to liver function remission, defined as two consecutive ALT values within normal range during the treatment period (i.e. excluding Week 28 follow-up visit), will be assessed by survival analysis. The time to the first of the two consecutive ALT values within normal range will be used for the TTR. The time in weeks will be calculated as (sample date – first dose date + 1)/7. For those reaching

remission, the Hodges-Lehmann estimator of the “location shift” between each dose group and placebo will be presented. The asymptotic (Moses) 95% confidence limits for the location shift will also be presented. The cumulative portion of the time-to-remission of each treatment group will be determined by Kaplan-Meier estimates. The time-to-remission will be analyzed using Cox proportional hazards model with treatment and diabetes stratum as explanatory variables. The following SAS code was used for the analyses of proportional hazards models:

```
proc phreg;  
  Model TIME*CENSOR(0) = TREATMENT DIABSTAT / risklimits;  
run;
```

Subjects who discontinue from the study before remission and subjects who complete the study without reaching remission will be assigned a TTR equal to the larger of the following two quantities:

- (Maximum TTR in days observed for all subjects in the study + 1 day) / 7;
- (Time to censoring (last ALT assessment during the treatment period) + 2 days) / 7.

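### One synopsis sentence stratifies allocation by baseline ALT, but every other statement that names a factor gives diabetes status: confirm which was used, reconcile, and consider baseline ALT in the remission analyses

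*Protocol*

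**What the plan says.** **Stratification.** The protocol synopsis, in its sample-size text on ALT change, says "Patients will be stratified into treatment arms based on threshold of baseline elevation of ALT" and defines two strata: below 2x ULN, and at least 2x but below 5x ULN. It gives no ULN for them. The Stratification row of the same synopsis gives diabetes status only, with HbA1c and medication definitions. Protocol 10.3.1 says "Patients will be stratified into treatment arms based diabetes status". SAP 4.2 says "Treatment allocation will be stratified by known diagnosis of diabetes status", and SAP 6.5 says "Randomization stratum (diabetic status) will also be summarized". Protocol 7.2 describes the randomisation schedule without naming a factor.

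**Models.** The synopsis paragraph with the ALT sentence also says the primary-endpoint model "incorporates the baseline measures as a covariate, the stratification factor and randomization treatment group". In the SAP:

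- MRI fat (6.9.1): ANCOVA "with treatment group and diabetes stratum as factors and baseline MRI value as a covariate".
- Time to remission (6.9.2.1): "Cox proportional hazards model with treatment and diabetes stratum as explanatory variables".
- Responders (6.9.2.1): Cochran-Mantel-Haenszel, adjusted for diabetes stratum.
- ALT, AST and GGT change (6.9.2.2): the same ANCOVA form, so the ALT model carries baseline ALT.

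For time to remission, the synopsis also foresees "fitting a Cox proportional hazard model with baseline variables as covariates", without naming the variables. Protocol 13.4.1.2 names treatment and diabetes status only.

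**The concern.** The current protocol text contains two incompatible stratification rules, and the SAP models follow one of them. A model should contain the factors used to stratify allocation. If one is left out, the variation it explains stays in the residual although the design has already balanced it. The standard errors are then too large.

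A second, separate issue does not depend on which rule was used. Remission is an absolute ALT threshold, so a patient's starting ALT sets how far it must fall. Neither the Cox model nor the responder analysis takes that into account, and with about 20 patients per arm a chance imbalance in baseline ALT would go uncorrected.

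**Working it through.** **1. Which rule is likely to have been used?** ALT stratification appears in one sentence. Diabetes stratification appears in the synopsis Stratification row, protocol 10.3.1, SAP 4.2 and SAP 6.5. Four further points suggest a leftover:

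- SAP 6.1 repeats the ALT power paragraph without the ALT sentence.
- The synopsis paragraph itself speaks of a single stratification factor.
- SAP 4.2 describes the schedule as already prepared and lists diabetes only.
- The protocol has another apparent leftover: 13.2.2 adjusts the Cochran-Mantel-Haenszel test for tumour size.

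A weak pointer the other way is protocol 13.2, which uses the plural for stratification factors but names none.

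**2. Do the ALT strata fit the eligible patients?** Inputs: screening ALT above 40 U/L (women) or 60 U/L (men), and exclusion above 250 U/L (protocol 8.1 and 8.2). The ULN must be assumed. The documents offer normal limits of 20/30 U/L (synopsis, SAP 5.2) and 40 U/L (SAP 5.2).

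| Assumed ULN | 2x | 5x | Lower stratum | Eligible ALT with no stratum |
|---|---|---|---|---|
| 40, both sexes | 80 | 200 | usable | 200 to 250 |
| 20, women | 40 | 100 | empty (entry is above 40) | 100 to 250 |
| 30, men | 60 | 150 | empty (entry is above 60) | 150 to 250 |

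Under either limit some eligible patients have no stratum, so the rule could not have been run as written.

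**3. What if ALT was used and then omitted from the ANCOVA?** The documents do not give the correlation r between ALT stratum and outcome, so a range is shown. Simulation: 60 patients, 1:1:1, permuted blocks of 3 within ALT by diabetes, each factor split evenly. ANCOVA with treatment, diabetes and a baseline covariate, with or without the ALT stratum. One active arm against placebo, two-sided 0.05, 8,000 runs per scenario, and an assumed effect of 0.9 SD for power.

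| r | Type I error, omitted | Included | Power, omitted | Included |
|---|---|---|---|---|
| 0 | 0.050 | 0.049 | 79% | 79% |
| 0.3 | 0.042 | 0.050 | 80% | 83% |
| 0.5 | 0.026 | 0.049 | 82% | 89% |
| 0.7 | 0.007 | 0.049 | 86% | 97% |

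Omission makes the test conservative and costs power. It does not raise the false-positive rate. Only the ANCOVA was simulated; the same direction is expected for the Cox and Cochran-Mantel-Haenszel analyses.

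**4. Why baseline ALT bears on remission.** The fall needed is (baseline - limit)/baseline. To get below 40 U/L, a man at the entry floor of 60 needs more than (60 - 40)/60 = 33%, and a patient at 250 needs more than (250 - 40)/250 = 84%. To get below 20 U/L, a woman at the entry floor of 40 needs more than (40 - 20)/40 = 50%, and one at 250 needs more than (250 - 20)/250 = 92%.

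**5. Are there enough events to use it?** Assumptions not in the documents: log-normal ALT with mean 90 and SD 40, entry ALT above 50 and at most 250, a 40% true fall on active treatment and none on placebo, and within-subject correlation 0.5 or 0.8. With 20 per arm and two consecutive values below 40 U/L, there are about 7 events or fewer per comparison. Both arms have an event in only 29 to 32% of simulated trials (correlation 0.5) or 15 to 17% (0.8). With a limit of 30 U/L for everyone, which is lenient for women, there are about 1 to 2 events, and at most 2.5% of trials have events in both arms. Over all simulated trials, with the active arms pooled, adding baseline ALT gained about 0 to 5 points of power.

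**6. The figure beside the ALT sentence.** The stated 73% power for ALT change says nothing about stratification. It is also not reproduced: 30/(50 x sqrt(2/20)) = 1.90 on 38 degrees of freedom gives 45.6%. That is a separate matter, and nothing here rests on it.

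**The case against.** The best reply is that this is one stray sentence. The synopsis contradicts it in its own Stratification row, the SAP drops it, and its strata do not work. On that reading the SAP models already contain the factor that was used. This largely stands. It cannot close the question, because the documents do not include the randomisation specification.

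It can also be said that the SAP Cox model does not depart from the protocol, since 13.4.1.2 specifies the same two terms. That is correct. The synopsis phrase on baseline variables does not name ALT, so it permits adjustment without promising this one. The two protocol statements do need to be reconciled.

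Finally, adjusting the remission analyses is an efficiency choice for secondary endpoints in an exploratory trial of 60 patients, and sparse events limit what it can deliver. This also stands, and the adjustment is put forward only as an inexpensive improvement. For the primary endpoint, nothing in the documents shows that ALT stratum predicts change in MRI fat once baseline MRI is in the model.

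**Conclusion.** The conflict between the stratification statements is real and in current text. It is most likely a drafting remnant.

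A reader might infer that the analysis does not match the randomisation. The documents do not support that: most of the evidence points to diabetes only, and in that case the models match. A reader might also fear false-positive results. Even if ALT was used, the error goes the other way. The cost for one active arm against placebo would be about 3, 7 or 11 points of power at assumed correlations of 0.3, 0.5 or 0.7 (83 - 80, 89 - 82, 97 - 86), for an assumed effect of 0.9 SD, and nothing at a correlation of 0.

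Leaving baseline ALT out of the remission analyses is a missed opportunity rather than an error. The gain from adding it is likely modest, and under the <20/<30 U/L definition the model may often not be estimable.

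**What to change.** 1. Before unblinding, confirm the stratification factor or factors from the randomisation (IVRS/IWRS) specification. Reconcile the two synopsis statements with protocol 7.2 and 10.3.1 and SAP 4.2.
2. If ALT was not used, delete the synopsis sentence. The SAP models can stay as they are on this point.
3. If ALT was used, state the ULN and how patients outside the defined strata were allocated. Add the ALT stratum to the MRI ANCOVA, the Cox model and the Cochran-Mantel-Haenszel analysis. Crossing it with diabetes gives four cells averaging 60/4 = 15 patients, or 5 per arm, so the stratified test will be thin.
4. In either case, add log baseline ALT to the time-to-remission Cox model, and report a responder analysis adjusted for baseline ALT and diabetes stratum as supportive. Make the synopsis and protocol 13.4.1.2 agree on the covariates. State in advance which model is reported if the adjusted one does not converge.

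The cost is one check, a few lines of wording and one covariate already measured in the Day 1 chemistry panel. The downside is instability when events are few, which is why the fallback should be written down beforehand.
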